### **3. Age and Reproductive Status**

- a) Adults, ages  $\geq 18$
- b) Women of childbearing potential (WOCBP) must have a negative serum or urine pregnancy test (minimum sensitivity 25 IU/L or equivalent units of HCG) within 24 hours prior to the start of study drug.
- c) Women must not be breastfeeding
- d) WOCBP should use an adequate method to avoid pregnancy for 5 months (30 days plus the time required for nivolumab to undergo five half-lives) after the last dose of investigational drug.
- e) Males who are sexually active with WOCBP must continue contraception for 7 months (90 days plus the time required for nivolumab to undergo five half-lives) after the last dose of investigational drug.
- f) Azoospermic males are exempt from contraceptive requirements. WOCBP who are continuously not heterosexually active are also exempt from contraceptive requirements, and still must undergo pregnancy testing as described in this section.

Investigators shall counsel WOCBP, and male subjects who are sexually active with WOCBP, on the importance of pregnancy prevention and the implications of an unexpected pregnancy. Investigators shall advise on the use of highly effective methods of contraception ([Appendix 6](#)), which have a failure rate of  $< 1\%$  when used consistently and correctly.

#### **3.3.2      *Exclusion Criteria***

##### **1. Target Disease Exclusions**

a) Subjects with:

- adenocarcinoma of the colon
- adenocarcinoma of the pancreas
- adenocarcinoma of the prostate
- adenocarcinoma of the rectum
- endometrial cancers with greater than 10% estrogen receptor positive pathology in the primary tumor
- epithelial ovarian cancer
- breast cancer that is ER, PR positive breast cancer OR HER2 positive OR triple-negative
- esophageal cancer
- gastric cancer
- 
- hepatocellular carcinoma
- Hodgkin's lymphoma
- leptomeningeal disease
- leukemia
- melanoma
- meningioma (low grade)
- multiple myeloma
- myelodysplastic syndrome
- non-Hodgkin's lymphoma (except primary CNS lymphoma without leptomeningeal disease)
- non-small cell lung cancer
- peritoneal carcinoma
- primary CNS lymphoma
- renal cell carcinoma
- small cell lung cancer
- squamous cell carcinoma of the head and neck
- squamous cell carcinoma of the skin
- urothelial bladder cancer (urothelial [transitional cell] histology or mixed histologies)
- carcinoma of unknown primary

**2. Medical History and Concurrent Diseases**

a) Subjects with previous malignancies (except non-melanoma skin cancers, and in situ cancers) are excluded unless a complete remission was achieved at least 2 years prior to study entry AND no additional therapy is required or anticipated to be required during the trial period.

- b) Active and untreated CNS metastases as determined by CT or MRI evaluation during screening and prior radiographic assessments. Subjects with CNS metastasis requiring corticosteroids are excluded from the trial.
- c) Previously treated spinal cord compression must be clinically stable for  $\geq$  6 weeks prior to first dose of nivolumab
- d) Uncontrolled pain
- e) Uncontrolled pleural effusion, pericardial effusion, or ascites requiring recurrent drainage procedures
- f) Uncontrolled hypercalcemia ( $> 1.5$  mmol/L ionized calcium or  $\text{Ca} > 12$  mg/dL or corrected serum calcium  $> \text{ULN}$ ) or symptomatic hypercalcemia requiring continued use of bisphosphonate therapy or denosumab
- h) Prior therapy with anti-PD-1, anti-PD-L1, anti-PD-L2, anti-CD137, or anti-CTLA-4 antibodies (including ipilimumab or any other antibody or drug specifically targeting T cell co-stimulation or checkpoint pathways).
- i) Subjects with an active, known or suspected autoimmune disease. Subjects with hypothyroidism only requiring hormone replacement, skin disorders (such as vitiligo, psoriasis, or alopecia) not requiring systemic treatment, type I diabetes mellitus, or conditions not expected to recur in the absence of an external trigger are permitted to enroll.
- j) Subjects with a condition requiring systemic treatment with either corticosteroids ( $> 10$  mg daily prednisone equivalent) or other immunosuppressive medications within 14 days of randomization. Inhaled or topical steroids, and adrenal replacement steroid doses  $> 10$  mg daily prednisone equivalent, are permitted in the absence of active autoimmune disease.
- k) Known history of positive test of human immunodeficiency virus (HIV) or known acquired immunodeficiency syndrome (AIDS). NOTE: Testing for HIV must be performed at sites where mandated locally (eg, Germany).
- l) Prior allogeneic bone marrow transplantation or prior solid organ transplantation
- m) Any disease, metabolic dysfunction, physical examination finding, or clinical laboratory finding giving reasonable suspicion of a condition or event that contraindicates the use of the investigational drug or that may affect the interpretation of the results or render the subject at high risk from treatment complication
- n) Subjects previously treated with investigational anticancer therapies less than 6 weeks prior to the first dose of nivolumab
- o) Evidence of significant uncontrolled concomitant disease that could affect compliance with the protocol or interpretation of results (eg, significant liver disease, cirrhosis, uncontrolled major seizure disorder, psychiatric disorders, superior vena cava syndrome)
- p) Significant cardiovascular disease, such as New York Heart Association cardiac disease (Class II or greater), myocardial infarction within 3 months before first dose of nivolumab, unstable arrhythmias or unstable angina
- q) Signs or symptoms of infection within 4 weeks before first dose of nivolumab, severe infections within 4 weeks before first dose of nivolumab including but not limited to

hospitalization for complications of infection, bacteremia or severe pneumonia, and/or received oral or IV antibiotics within 2 weeks before first dose of nivolumab

- r) All toxicities attributed to prior anti-cancer therapy other than alopecia and fatigue must have resolved to Grade 1 (NCI CTCAE version 4) or baseline before administration of study drug. Subjects with toxicities attributed to prior anti-cancer therapy which are not expected to resolve and result in long lasting sequelae, such as neuropathy after platinum based therapy, are permitted to enroll.
- s) Major surgical procedure within 28 days before first dose of nivolumab or anticipation of need for a major surgical procedure during the course of the study
- t) Treatment with botanical preparations (eg, herbal supplements or traditional Chinese medicines) intended for general health support or to treat the disease under study within 2 weeks prior to randomization/treatment. Refer to [Section 3.4.1](#) for prohibited therapies.

### **3. Physical and Laboratory Test Findings**

- a) Any positive test for hepatitis B virus or hepatitis C virus indicating acute or chronic infection, and/or detectable virus
- b) Positive test for human immunodeficiency virus (HIV)

### **4. Allergies and Adverse Drug Reaction**

- a) History of allergy or hypersensitivity to study drug components
- b) Known hypersensitivity to dacarbazine (DTIC)

### **5. Other Exclusion Criteria**

- a) Prisoners or subjects who are involuntarily incarcerated. (Note: under specific circumstances a person who has been imprisoned may be included as a subject. Strict conditions apply and Bristol-Myers Squibb approval is required.)
- b) Subjects who are compulsorily detained for treatment of either a psychiatric or physical (eg, infectious disease) illness

Eligibility criteria for this study have been carefully considered to ensure the safety of the study subjects and that the results of the study can be used. It is imperative that subjects fully meet all eligibility criteria.

#### **3.3.3      *Women of Childbearing Potential***

[figure not shown]
Women of childbearing potential (WOCBP) is defined as any female who has experienced menarche and who has not undergone surgical sterilization (hysterectomy or bilateral oophorectomy or bilateral salpingectomy) and is not postmenopausal. Menopause is defined as 12 months of amenorrhea in a woman over age 45 years in the absence of other biological or physiological causes. In addition, females under the age of 55 years must have a serum follicle stimulating hormone, (FSH) level  $> 40$  mIU/mL to confirm menopause.

\*Females treated with hormone replacement therapy, (HRT) are likely to have artificially suppressed FSH levels and may require a washout period in order to obtain a physiologic FSH level. The duration of the washout period is a function of the type of HRT used. The

duration of the washout period below are suggested guidelines and the investigators should use their judgement in checking serum FSH levels.

- 1 week minimum for vaginal hormonal products (rings, creams, gels)
- 4 week minimum for transdermal products
- 8 week minimum for oral products

Other parenteral products may require washout periods as long as 6 months. If the serum FSH level is  $> 40$  mIU/ml at any time during the washout period, the woman can be considered postmenopausal.

### **3.5 Discontinuation of Subjects following any Treatment with Study Drug**

Subjects MUST discontinue investigational product (and non-investigational product at the discretion of the investigator) for any of the following reasons:

- Subject's request to stop study treatment
- Any clinical adverse event (AE), laboratory abnormality or intercurrent illness which, in the opinion of the investigator, indicates that continued participation in the study is not in the best interest of the subject
- Termination of the study by Bristol-Myers Squibb (BMS)
- Loss of ability to freely provide consent through imprisonment or involuntarily incarceration for treatment of either a psychiatric or physical (eg, infectious disease) illness. (Note: Under specific circumstances, a participant who has been imprisoned may be permitted to continue as a participant. Strict conditions apply, and BMS approval is required).
- Any event found in the Discontinuation criteria as outlined in [Section 4.5.3](#).

Subjects discontinuing study treatment will remain on study for documentation of progression and death for up to one year.

In the case of pregnancy, the investigator must immediately notify the Sponsor or designee of this event. In most cases, the study drug will be permanently discontinued in an appropriate manner (eg, dose tapering if necessary for subject safety). Please contact the Sponsor or designee within 24 hours of awareness of the pregnancy. If the investigator determines a possible favorable benefit/risk ratio that warrants continuation of study drug, a discussion between the investigator and the Sponsor or designee must occur.

All subjects who discontinue study drug should comply with protocol specified follow-up procedures as outlined in [Section 5](#). The only exception to this requirement is when a subject withdraws consent for all study procedures including post-treatment study follow-up or loses the ability to consent freely (ie, is imprisoned or involuntarily incarcerated for the treatment of either a psychiatric or physical illness).

If study drug is discontinued prior to the subject's completion of the study, the reason for the discontinuation must be documented in the subject's medical records and entered on the appropriate case report form (CRF) page.

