### **3.6 Post-Study Drug Study Follow up**

In this study, overall survival is a key endpoint of the study. Post-study follow-up is of critical importance and is essential to preserving subject safety and the integrity of the study. Subjects who discontinue study drug must continue to be followed for collection of outcome and/or survival follow-up data as required and in line with Section 5 until death or the conclusion of the study.

BMS may request that survival data be collected on all treated/randomized subjects outside of the protocol defined window ([Table 5.1-4](#)). At the time of this request, each subject will be

contacted to determine their survival status unless the subject has withdrawn consent for all contacts or is lost to follow-up.

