**Table 5.1-4: Follow-Up Assessments - All Subjects CA209627**

Procedure	Follow-Up Visits X01 (Day 35) ( $\pm 7$ Days) and X02 (Day 100) a ( $\pm 7$ Days) after last dose	Survival Follow-Up Visits b Every 12 weeks	Notes
Efficacy Assessments			
Radiographic Tumor Assessment	See notes		Only for subjects without progression and no longer on study therapy. If subject starts subsequent treatment, no assessment required  Subjects with a history of brain metastasis may have surveillance MRI approximately every 12 weeks or sooner if clinically indicated
Subject Status			
Survival Status	X	X	Every 3 months after X02; may be accomplished by visit or phone contact, to update survival information and assess subsequent anti-cancer therapy.

NOTES:

a Subjects must be followed for at least 100 days after last dose of study treatment. Follow-up visit #1 occurs approximately 35 days ( $\pm 7$  days) after the last dose or coinciding with the date of discontinuation ( $\pm 7$  days) if date of discontinuation is greater than 30 days after last dose. Follow-up visit #2 occurs approximately 100 days ( $\pm 7$  days) from last dose

b Survival Follow-up visits to occur every 3 months from Follow-up Visit 2. At the time of this request, each subject will be contacted to determine their survival status unless the subject has withdrawn consent for all contact. Vital signs not required if follow-up is performed via telephone contact.

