Radiographic tumor response will be assessed at Week 8 ( $\pm$  5 days), Week 16 ( $\pm$  5 days), and Week 28 ( $\pm$  5 days), then every 12 weeks ( $\pm$  5 days) until disease progression, beyond progression, lost to follow-up, or withdrawal of consent. Tumor assessments for all subjects should continue as per protocol even if dosing is interrupted. Tumor measurements should be made by the same investigator or radiologist for each assessment whenever possible. Change in tumor measurements and tumor response to guide ongoing study treatment decisions will be assessed by the investigator using the RECIST 1.1 criteria (see [Appendix 4](#) for details of RECIST 1.1). Independent adjudication will resolve equivocal interpretations of imaging results.

*Local radiologic assessment of tumor measurements will be used during the study for clinical management and investigator-assessed disease progression using RECIST 1.1 criteria. The same imaging modality used in screening must be used in all subsequent imaging assessments. Any incidental findings of potential clinical relevance that are not directly associated with the objectives of the protocol should be evaluated and handled by the study investigator as per standard medical/clinical judgment.*

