Time to response (TTR) is defined as the time from first dosing date to the date of the first confirmed response, as assessed by investigator. Summary statistics of TTR will be provided for participants who achieve PR or CR.

7.5.3.3 *Clinical Benefit Rate*

Clinical benefit rate (CBR) is defined as the number of participants with a best overall response of confirmed CR or PR, or stable disease divided by the number of all treated subjects. CBR will be provided along with the corresponding 2-sided 95% confidence intervals using the method based on the Binomial distribution.

7.5.3.4 *Overall Survival*

The OS rate at 1 year will be calculated by tumor group. OS is defined as time from the date of enrollment to the date of death. Subjects who did not die by the end of the study will be censored at the last known date alive.

Time to event distribution will be estimated using Kaplan Meier techniques. This will be done for OS. Median OS along with 95% CI will be constructed based on a log-log transformed CI for the survivor function. Rates at 1-year will be derived from the Kaplan Meier estimate and corresponding confidence interval will be derived based on Greenwood formula for variance derivation and on log-log transformation applied on the survivor function.

The status of subjects who are censored in the OS KM analysis will be tabulated for each treatment group using following categories:

- On-study: (on-treatment and not progressed, on-treatment progressed, in follow-up)
- Off-study: (lost to follow-up, withdraw consent, etc.)

7.6 *Safety*

Unless otherwise specified, the safety data will be presented by tumor group.

Whenever appropriate, analysis of all safety data will be performed by following the BMS nivolumab Core Safety SAP (version 4.0)¹ and the comprehensive specifications for the

development of data displays for tables, listings and graphs should follow the BMS nivolumab Core Safety Data Presentation Plan (DPP)².

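### Protocol Section 3.5 limits follow-up after treatment stops to one year, while Section 3.6, Section 5.3.1 and Table 5.1-4 set no such limit; applied literally, the limit could bias median OS upward and cut off long or late response durations.

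*Protocol*

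**What the plan says.** Protocol Section 3.5, on subjects who stop study drug: "Subjects discontinuing study treatment will remain on study for documentation of progression and death for up to one year". The start of the year is not given. The same section then says: "All subjects who discontinue study drug should comply with protocol specified follow-up procedures as outlined in" Section 5.

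Protocol Section 3.6 calls overall survival a key endpoint and requires that subjects who stop drug continue to be followed for outcome and/or "survival follow-up data as required and in line with Section 5 until death or the conclusion of the study". It also lets the sponsor request survival data outside the protocol window.

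Section 5 carries no one-year limit:
- Table 5.1-4, survival status: "Every 3 months after X02; may be accomplished by visit or phone contact, to update survival information". No last contact is stated.
- Table 5.1-4, imaging after treatment: "Only for subjects without progression and no longer on study therapy", and not required once a subsequent treatment starts.
- Section 5.3.1, imaging every 12 weeks after Week 28: "until disease progression, beyond progression, lost to follow-up, or withdrawal of consent".

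On the analysis side, SAP Section 7.5.3.4 plans the 1-year OS rate and median OS with a 95% CI, with this censoring rule: "Subjects who did not die by the end of the study will be censored at the last known date alive". SAP Section 7.5.3.1 plans Kaplan-Meier probabilities of response lasting beyond 6, 9 and 12 months. Neither provides for a cut-off tied to the date treatment stopped.

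**The concern.** Two current sections govern the same subjects and the same data but end follow-up at different times. A site that obeys Section 3.5 literally could close a subject's record a year after the last treatment; a site that obeys Section 3.6 would not.

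The statistical consequence comes from the form of the limit. Counted from treatment stop, the last possible observation is treatment duration plus 12 months. Subjects who stop early, typically because of progression, leave the risk set first, and those who stayed longer on drug remain. Kaplan-Meier estimation assumes that censoring carries no information about prognosis, and here it would. The expected direction is upward for OS beyond 12 months. Response durations would also be cut off at the limit, and later scans that were never taken cannot be recovered.

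**Working it through.** The plan gives no figure for this point, so there is nothing to reproduce. The check is timeline arithmetic plus an illustrative simulation on assumed survival times.

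**1. OS follow-up under Section 3.5.** Reading the year as starting at treatment stop (an inference), the limit from first dose is treatment duration + 12 months:
- single dose: 0 + 12 = 12
- stop at month 4: 4 + 12 = 16
- stop at month 12: 12 + 12 = 24
- full 24 months (maximum in Section 3.1): 24 + 12 = 36

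The earliest limit is 12 months, so the 1-year OS rate is covered under either rule.

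**2. OS follow-up under Section 3.6.** Enrollment takes about 24 months (Section 3.1), treatment up to 24 months, and the second follow-up visit is at 100 days. Using the SAP conversion of 30.4375 days per month, 24 + 24 + 100/30.4375 = 51.3 months. An early enrollee could therefore be followed to about month 51 or later.

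**3. Duration of response (DOR).** Follow-up available = (stop day + 365.25 − first-response day) / 30.4375.
- Response on the day of stopping: 365.25/30.4375 = 12.0 months; an earlier response gives more.
- Stop week 16, response week 28: (112 + 365.25 − 196)/30.4375 = 9.2 months.
- Stop week 8, response week 28: (56 + 365.25 − 196)/30.4375 = 7.4 months.
- Stop after the first dose, response week 28: (365.25 − 196)/30.4375 = 5.6 months.

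Anyone who responds on or before stopping keeps at least 12 months. Only a response that first appears after stopping falls short of the 12-month landmark.

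**4. Size of the OS effect.** Assumptions, none from the documents: exponential time to progression; exponential survival after progression; no death before progression; treatment stops at progression or month 24; every site censors at stop + 12 months. One million simulated subjects per row; times in months.

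| Assumed medians: on treatment / after | 12-month OS, limited and true | Median OS, limited | Median OS, true | Share of deaths captured under limit |
|---|---|---|---|---|
| 3 / 9 | 56.4% both | 13.8 | 13.7 | 60.3% |
| 3 / 12 | 64.6% both | 16.9 | 16.7 | 50.0% |
| 3 / 18 | 74.4% both | 23.1 | 22.7 | 37.0% |
| 6 / 9 | 69.0% both | 18.5 | 18.0 | 58.5% |
| 6 / 12 | 75.0% both | 22.5 | 21.3 | 48.4% |
| 6 / 18 | 82.0% both | 30.5 | 27.5 | 35.8% |

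The largest shift, 3.0 months, depends on a modeling detail. If survival after treatment is counted from the stop itself, even for those stopped at month 24, the last row gives 28.5 against 27.2, a shift of 1.3.

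A separate run added an administrative study end between 27.3 and 51.3 months, with medians of 3 to 5 months to progression and 6 to 15 months afterwards. Deaths captured fell from 75–97% under Section 3.6 to 42–75% under the limit. Median OS rose by 0 to 1.4 months. The 12-month OS rate was again identical.

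**The case against.** The strongest reply is that the protocol largely answers the question itself. Section 3.5 sends the same subjects to Section 5, which has no one-year limit; Section 3.6 is worded as a requirement; and the sponsor may ask for survival data outside the window. One sentence stands against several passages that agree. This makes Section 3.5 the outlier and makes universal application of the limit unlikely, so the simulated shifts are an upper case within the assumed range. It does not remove the conflict: no text gives precedence, the sponsor's request is optional, and it concerns survival status, not missed scans.

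Second, the start of the year is inferred. If it ran from first dose, the figures above would not apply. That objection stands, and it is also a reason to state the start date.

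Third, groups are normally limited to 25 subjects. Near 50% survival the standard error of an OS rate with complete follow-up is √(0.5 × 0.5/25) = 10 percentage points, so in most scenarios the bias is small against sampling error. This also stands.

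A reader might infer more than the documents support:
- **That median OS becomes unobservable.** It remained estimable in every scenario.
- **That inflated 24-month OS is a finding.** The same simulation overstates it by about 1 to 3.5 points, but the plan names no 24-month OS landmark.
- **That 12-month DOR is lost in general.** It is lost only for a response first seen after stopping, without progression or new therapy in between, which is an edge case. Those subjects would be censored, and the rate would be estimated from the others.

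**Conclusion.** The contradiction is real in the current text, and its consequences are limited. The primary ORR analysis is not shown to be affected, and the named secondary endpoint, OS at one year, is unaffected when the year is counted from treatment stop. What is exposed is median OS, with an upward bias of about 0 to 3 months under the assumed medians (3 to 6 months on treatment, 9 to 18 after) if every site applied the limit; the number of deaths captured; DOR beyond 12 months; and 12-month DOR in the few late responders. These sizes rest on assumed exponential times and on an inferred start of the year. The documents do not show that any site follows the limit. This is a minor inconsistency that is worth correcting because correction is cheap.

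**What to change.** Reconcile the passages in one amendment:
1. In Section 3.5, delete the one-year limit and cross-refer to Section 3.6 and Table 5.1-4.
2. State one finite end of survival follow-up, with the date it is counted from. Deleting the phrase alone is not enough. Section 3.1 defines end of trial as the last scheduled procedure for the last subject, and Table 5.1-4 names no last survival contact, so follow-up until study end has no defined stopping point.
3. If a limit is intended, state it with its start date in Sections 3.5 and 3.6, Section 5.3.1 and Table 5.1-4, and restrict the SAP's OS and DOR summaries to the period it covers.

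The cost is a short wording change in Section 3.5 plus one added sentence on the end of follow-up. No new procedure is needed, since the 3-monthly contacts and the post-treatment imaging are already scheduled. The third option would also need a SAP edit.
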